4.2.4. Time to Response

Some time (months) to responses are defined as follows:

- Time to CR (TTCR) is defined as the time from the date of first study drug administration from Cycle 1 in continuous cycle (i.e. not from the date of single oral dose from the PK week for the dose escalation part) to the date of first CR. Only patients with CR will be included in this analysis.
- Time to CRh (TTCRh) is defined as the time from the date of first study drug administration from Cycle 1 in continuous cycle (i.e. not from the date of single oral dose from the PK week for the dose escalation part) to the date of first CRh. Only patients with CRh will be included in this analysis.
- Time to cCR-1 (TTcCR1) is defined as the time from the date of first study drug administration from Cycle 1 in continuous cycle (i.e. not from the date of single oral dose from the PK week for the dose escalation part) to the date of first cCR-1. Only patients with cCR-1 will be included in this analysis.
- Time to cCR-2 (TTcCR2) is defined as the time from the date of first study drug administration from Cycle 1 in continuous cycle (i.e. not from the date of single oral dose from the PK week for the dose escalation part) to the date of first cCR-2. Only patients with cCR-2 will be included in this analysis.
- Time to cCR-3 (TTcCR3) is defined as the time from the date of first study drug administration from Cycle 1 in continuous cycle (i.e. not from the date of single oral dose from the PK week for the dose escalation part) to the date of first cCR-3. Only patients with cCR-3 will be included in this analysis.

- Time to objective response (TTOR) is defined as the time from the date of first study drug administration from Cycle 1 in continuous cycle (i.e. not from the date of single oral dose from the PK week for the dose escalation part) to the date of first objective response (CR_{MRD}-, CR, CRh, CRi, MLFS, or PR). Only patients with objective response will be included in this analysis.

The time (months) to response is generally calculated as (date of first occurrence of interested response category - date of first study drug administration from Cycle 1 + 1)/30.4375.

4.2.5. Event-free Survival

Event-free survival (EFS) is defined as the time from date of first study drug administration from Cycle 1 in continuous cycle (i.e. not from the date of single oral dose from the PK week for the dose escalation part) to treatment failure, relapse from CR (including CR_{MRD}-, CR, CRh and CRi), or death due to any cause, whichever occurs first. EFS analysis will take competitor Ivosidenib Phase III EFS definition and censoring rules as reference ([Xu et al, 2020](#)). Treatment failure is defined as failure to achieve CR (including CR_{MRD}-, CR, CRh and CRi) by Week 24. Subjects who do not achieve CR (including CR_{MRD}-, CR, CRh and CRi) by Week 24 will be considered to have had an event at Day 1 of first study drug administration from Cycle 1 (i.e. not from the date of single oral dose from the PK week for the dose escalation part). For the remaining CR responders (including CR_{MRD}-, CR, CRh and CRi), the event time will be the time of either disease relapse or death due to any cause, whichever occurs first. A response of CR (including CR_{MRD}-, CR, CRh and CRi) represents both disease control and establishment of hematopoiesis in subjects with AML and is an important predictor of OS ([Dombret et al, 2015](#)). Event-free survival will be censored upon initiation of a subsequent anticancer therapy.

The outcome (event or censor), type of event and the date of event or censoring to be considered for the EFS are presented in [Table 4](#).

Table 4 Outcome and Event or Censoring Dates for EFS

Rule	Situation	Date of Event or Censoring	Outcome
1	CR by 24 weeks ^a then relapse between scheduled visit or after one missing tumor assessment visit	Date of relapse	Event (relapse)
2	CR by 24 weeks ^a then death (no relapse) between scheduled visit or after one missing tumor assessment visit	Date of death	Event (death)
3	On treatment \geq 24 weeks without CR by 24 weeks ^a	Date of first administration of study treatment	Event (TF, on treatment \geq 24 weeks without CR)
4	Treatment discontinuation prior to 24 weeks, without CR by 24 weeks ^a	Date of first administration of study treatment	Event (TF, treatment discontinuation prior to 24 weeks without CR)
5	On treatment $<$ 24 weeks without CR and active in study	Date of the last adequate disease assessment	Censored
6	CR by 24 weeks ^a then start subsequent anticancer therapy (prior to death or relapse or no relapse)	Date of the last adequate disease assessment documenting no relapse prior to start of subsequent anticancer therapy or missed response assessments	Censored
7	CR by 24 weeks ^a then death or relapse after missed or inadequate two or more consecutive tumor assessments		Censored
8	CR by 24 weeks ^a and neither relapse nor death		Censored
9	No baseline or post-baseline adequate disease assessment	Date of first administration of study treatment	Censored

CR: including CRMRD-, CR, CRh and CRi; EFS = event-free survival; TF = treatment failure.

^aBased on the protocol schedule of assessments, “+1 week window” is allowed.

Note: The same algorithm for determination of one and two/more consecutive missing or inadequate assessments can be found in [Section 4.2.3..](#)

Reasons for censoring are included in [Table 5](#) following the hierarchy.

Table 5 EFS Censoring Reasons and Hierarchy

Hierarchy	Condition	Censoring Reason
1	No baseline or post-baseline adequate disease assessment	No baseline or post-baseline tumor assessments
2	On treatment $<$ 24 weeks without CR and active in study	On treatment $<$ 24 weeks, active in study
3	CR by 24 weeks then start subsequent anticancer therapy	CR by 24 weeks, start subsequent anticancer therapy
4	CR by 24 weeks then death or relapse after missed or inadequate two or more consecutive tumor assessments	CR by 24 weeks, missed or inadequate two or more consecutive tumor assessments
5	CR by 24 weeks, no relapse or death, lost to follow-up	CR by 24 weeks, lost to follow-up

6	CR by 24 weeks, no relapse or death, withdrawal by subject from the study	CR by 24 weeks, withdrawal by subject
7	CR by 24 weeks, no relapse or death, ongoing in study	CR by 24 weeks, ongoing without relapse or death

CR: including CRMRD-, CR, CRh and CRi; EFS = event-free survival.

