- Primary refractory AML unsuitable for intensive chemotherapy or venetoclax-based regimen or target agents;
- Relapsed/refractory AML that has progressed on prior IDH treatment

The sponsor, in consultation with SRC, may decide to increase or decrease the number of enrolled patients in each cohort, depending on preliminary clinical response, safety signals, or operational feasibility. Patients who are not efficacy evaluable in any cohort may be replaced.

The overall study schema is presented in [Figure 1](#).

Figure 1 Study Schema

Any patient who discontinues treatment should be encouraged to return to the study site for an End of Treatment (EOT) Visit and continue with the remaining study visits. Patients must be discontinued from treatment for disease progression, withdrawal of consent, intolerable toxicity, repeated non-compliance or poor compliance, commencement of other antitumor treatment during the study, pregnancy, loss to follow-up, termination of the study by the sponsor, death, or end of the study.

Patients who discontinue the study drug due to reasons other than disease progression, death, lost to follow-up, or withdrawal of consent will remain on study for tumor assessments and will be followed every 12 weeks (± 14 days) from the EOT visit or last assessment, until disease progression, initiation of new anticancer therapy, withdrawal of consent, lost to follow-up, death, conditions are met, or the end of the study, whichever comes first. Survival information can be obtained via phone and information will be documented in the source documents and relevant case report forms (CRFs). The end of study is defined as the date on which all patients have their last visit or 1 year after the last patient has their first visit, whichever comes first.

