4.2. Efficacy Endpoints

4.2.1. Best Overall Response

Assessment of anti-tumor response for patients with AML will be conducted according to 2017 European Leukemia Net (ELN) criteria (Döhner et al, 2017). Best overall response (BOR) is defined as the best response during the anti-tumor evaluation period, which will be determined using time point responses (TPRs) from date of the first dose of study treatment from Cycle 1 in continuous cycle (i.e. not from the date of single oral dose from the PK week for the dose escalation part) up until the last evaluable TPR prior to or on the date of (i) disease progression (at least 2 cycles of study drug should be administered to determine PD) / relapse according to the 2017 ELN criteria, or death; or (ii) withdrawal of consent or lost to follow-up; or (iii) receiving subsequent anti-cancer therapy, whichever is earlier.

The hierarchical order of these response categories is complete response with negative minimal residual disease (CR_{MRD-}) > complete response (CR) > complete response with partial hematological recovery (CRh) > complete response with incomplete count (CRI) > morphologically leukemia-free state (MLFS) > partial response (PR) > stable disease (SD) > progressive disease (PD) > NE (not evaluable), where CR_{MRD-} , CR and CRI are based on investigator assessment of response, and CRh will be derived from relevant data including investigator-collected bone marrow and hematology data by medical team as external file, as CRh is not defined in ELN 2017. This order will be used to derive the BOR. For example, a patient who has 4 anti-tumor assessments during the anti-tumor evaluation period with response being MLFS, PR, SD, and PD respectively, then the BOR for this patient will be MLFS.

Of note, for the BOR being SD, it is expected that the duration of SD lasts for at least 3 cycles, for example, if a patient only has one tumor assessment at 2 cycles with response being SD, then, the BOR for this patient will be NE instead. For the BOR being PD, at least 2 cycles of study drug should be administered, for example, if a patient only has one tumor assessment at 1 cycle of study drug with response being PD, then, the BOR for this patient will be NE instead.

Moreover, subjects who do not have post-dose tumor assessment, but have clinical progression as noted by the investigator or have died due to any cause before their second post-dose tumor assessment, BOR will be PD.

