4.2.7. Progression-free Survival

Progression-free Survival (PFS) is defined as the time (months) from the start of study treatment from Cycle 1 in continuous cycle (i.e. not from the date of single oral dose from the PK week for the dose escalation part) to disease progression, or relapse, or death due to any cause, whichever occurs first. More specifically, PFS will be determined using all the assessment data up until the last evaluable visit prior to or on the date of

- (i) disease progression (at least 2 cycles of study drug should be administered to determine PD) or relapse as defined by 2017 ELN criteria for AML patients, or
- (ii) withdrawal of consent; or lost to follow-up, or
- (iii) receiving subsequent anti-tumor therapy, whichever is earlier.

Patients without report of PD or death due to any cause at the time of analysis are censored as described in [Table 7](#) below.

Table 7 Outcome and Event or Censoring Dates for PFS

Rule	Situation	Date of Progression or Censoring	Outcome
------	-----------	----------------------------------	---------

1	PD/relapse documented between schedule tumor assessment visit or after one missing tumor assessment visit	Date of first documented disease progression/relapse	Event
2	Death without PD/relapse between schedule tumor assessment visit or death on or before the second scheduled visit or death after one missing tumor assessment visit	Date of death	Event
3	No baseline or post-baseline tumor assessments available and subject dose not die	Date of first administration of study treatment	Censored
4	No death or PD/relapse by the time of data cut-off for final analysis	Date of last adequate tumor assessment prior to or on analysis data cutoff date	Censored
5	Early discontinuation (lost to follow-up or withdrawal of consent) of study without death or PD/relapse	Date of last adequate tumor assessment	Censored
6	Subsequent anti-tumor therapy started prior to PD/relapse or death	Date of last adequate assessment prior to or on date of initiation of subsequent therapy visit	Censored
7	PD/relapse or death after missed or inadequate two or more consecutive tumor assessment visits	Date of last adequate tumor assessment prior to missed visits or date of first administration of study treatment (if no post-baseline tumor assessment)	Censored

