5.2.9.2. DoCR/DoOR, EFS, PFS, and OS

For the time to event endpoints, such as various DoCRs/DoOR defined in [Section 4.2.3](#), EFS and EFS for patients with CR by 24 weeks (if data allowed) defined in [Section 4.2.5](#), OS defined in [Section 4.2.6](#), and PFS defined in [Section 4.2.7](#), the 25%, 50% (median), and 75% percentile of time-to-event will be estimated using Kaplan-Meier method with their corresponding 95% CI which are calculated from a log-log transformation based on the method by [Brookmeyer and Crowley \(1982\)](#). For PFS and OS, additionally, estimates will be provided for the survival probability along with their 95% CIs which are calculated using linear transformation based on the

method by [Brookmeyer and Crowley \(1982\)](#) at selected landmarks, for example, at 3, 6, 9, 12, and 18 months. The Kaplan-Meier plots will be produced for PFS and OS.

The duration of follow-up for PFS will be summarized by reversed Kaplan-Meier method (i.e. using different censoring rule which reverses censoring indicator of PFS, i.e. patients who progressed or died in PFS analysis will be censored at the date of progression or death, patients who are censored in PFS analysis will be assigned indicator of “event” with the same duration for PFS.) to calculate median, first and third quartiles and 95% CIs. The duration of follow-up for DoCR/DoOR, EFS, OS will be summarized similarly.

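### EFS: an early death or early stop with no adequate disease assessment is both an event (Rule 4) and censored (Rule 9) at first dose, and the SAP does not say which rule prevails

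*SAP*

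**What the plan says.** SAP 4.2.5 counts death from any cause as an EFS event. Patients without CR by Week 24 "will be considered to have had an event at Day 1 of first study drug administration from Cycle 1". CR here covers CR without MRD, CR, CRh and CRi.

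Table 4 then assigns outcomes:
- **Rule 4:** "Treatment discontinuation prior to 24 weeks, without CR by 24 weeks" is an event (treatment failure), dated at first dose. It does not require an adequate assessment.
- **Rule 9:** "No baseline or post-baseline adequate disease assessment" is censored, also dated at first dose. It has no exception for death or discontinuation.

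Table 5 puts the Rule 9 condition first, but it ranks reasons for censoring only and contains no event rule.

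SAP 2.2 lists the reasons for stopping treatment, which include "loss to follow-up, termination of the study by the sponsor, death, or end of the study". A death on treatment is therefore a discontinuation in the sense of Rule 4.

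The SAP settles the same early death for two other endpoints. In PFS (Table 7), Rule 3 censors only when "No baseline or post-baseline tumor assessments available and subject dose not die", and Rule 2 counts "death on or before the second scheduled visit" as an event. For best overall response (SAP 4.2.1), patients who have no post-dose assessment but "have died due to any cause before their second post-dose tumor assessment, BOR will be PD".

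**The concern.** The first scheduled on-treatment evaluation is Cycle 3 Day 1, at Week 8 (Protocol 6.1.14). A patient who dies before then, or stops without an adequate end-of-treatment assessment, satisfies Rule 4 and Rule 9 together: same date, opposite outcomes. As written, one early death can be PD for best response, an event for PFS and a censored observation for EFS.

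The direction matters. Early death is the worst outcome, and censoring it at Day 1 makes EFS look better. For EFS, SAP 5.2.9.2 plans that "the 25%, 50% (median), and 75% percentile of time-to-event will be estimated using Kaplan-Meier method", and SAP 5.1.1 reports efficacy by dose level. In small dose cohorts one or two patients can change a reported quartile, and a reader of the results could not tell which rule had been used.

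A second, rarer overlap comes from the baseline half of the Rule 9 wording. A patient with no adequate baseline but a documented CR, followed by relapse or death, meets Rule 9 and also Rule 1 or 2.

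**Working it through.** The SAP gives no EFS figure to reproduce. The check is a reading of the rules, followed by the effect on the planned quartiles.

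**1. The rules for one patient: dies in Week 5, no post-baseline assessment**

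| Source | Outcome | Date |
|---|---|---|
| EFS definition (death; no CR by Week 24) | Event | Day 1 (no CR) |
| Table 4 Rule 4 (discontinued before 24 weeks, no CR) | Event | First dose |
| Table 4 Rule 9 (no adequate assessment) | Censored | First dose |
| PFS Table 7 Rule 2 | Event | Date of death |
| Best overall response, SAP 4.2.1 | PD | – |

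Nothing in SAP 4.2.5 orders event rules against censoring rules.

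**2. Effect on the Kaplan-Meier estimate**

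Let n be the cohort size, c the number with CR by 24 weeks, and k the number of early unassessed deaths or stops. All other patients are Day 1 treatment failures. By the usual convention, patients censored on Day 1 are still at risk for Day 1 events.

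- Rule 4 first: S(Day 1) = c/n
- Rule 9 first: S(Day 1) = (c + k)/n
- Difference: k/n. For one patient this is 1/3 = 33 points, 1/6 = 17 points or 1/12 = 8 points.

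The cohort sizes come from Protocol 4.1.1: at least 3 per level, 3 to 6 for the preliminary DLT assessment, extendable to 12. The 75th percentile leaves Day 1 when S(Day 1) exceeds 0.25, and the median when it exceeds 0.50.

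| n | c | k | Rule 4 first | Rule 9 first | What moves |
|---|---|---|---|---|---|
| 3 | 0 | 2 | 0 | 2/3 = 0.67 | Median: Day 1 to not reached, with no responder |
| 3 | 1 | 1 | 1/3 = 0.33 | 2/3 = 0.67 | Median: Day 1 to the responder's event time |
| 6 | 1 | 1 | 1/6 = 0.17 | 2/6 = 0.33 | 75th percentile |
| 6 | 1 | 3 | 1/6 = 0.17 | 4/6 = 0.67 | Median |
| 12 | 2 | 2 | 2/12 = 0.17 | 4/12 = 0.33 | 75th percentile |
| 12 | 2 | 5 | 2/12 = 0.17 | 7/12 = 0.58 | Median |

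If a program instead drops the Day 1 censored patients from the risk set, the estimate is c/(n − k) and the shift is smaller. For n=10, c=2 and k=1 to 4, it is 0.22, 0.25, 0.29 and 0.33, against 0.30, 0.40, 0.50 and 0.60 under the usual convention. Rule 4 first gives 0.20 throughout.

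**3. How often a quartile would move (assumption range, n=6)**

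Assume a share q of patients are early unassessed deaths and 20% of the rest reach CR. The 20% is the planning CR rate in Protocol 9.1.2.2, applied here to the wider EFS definition of CR. The number with CR, the number unassessed and the number of failures are then multinomial with probabilities 0.2(1 − q), q and 0.8(1 − q).

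| q | 75th percentile leaves Day 1 (c ≤ 1, c + k ≥ 2) | Median leaves Day 1 (c ≤ 3, c + k ≥ 4) |
|---|---|---|
| 10% | 0.24 | 0.04 |
| 20% | 0.45 | 0.12 |
| 32% | 0.65 | 0.26 |

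**4. Where the 32% comes from (scale only)**

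Protocol 2.3.1 quotes a median OS of about 1.5 months and 8% one-year survival in refractory AML. Week 8 is 56/30.4375 = 1.84 months. Under an exponential curve:
- from 8% at one year: 1 − exp(−1.84 × (−ln 0.08)/12) = 0.32 dead by Week 8;
- from the 1.5-month median: 1 − 2^(−1.84/1.5) = 0.57.

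The second curve implies 2^(−12/1.5) = 0.4% one-year survival, so the two figures do not fit one exponential and 0.57 is an upper bound. Both count all deaths before Week 8, including any with an adequate assessment, so q = 32% is a high-end entry.

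**The case against.** The strongest reply is that a consistent reading exists. The EFS definition points to an event without exception, Rule 4 repeats it, and Rule 9 comes last. Read as a residual rule, Rule 9 still does something: a patient active on treatment for less than 24 weeks with no assessment has no date under Rule 5, and Rule 9 supplies one. On that reading EFS is not biased. This is a sensible reading, but the SAP does not state it, and the first place given to the same condition in Table 5 invites the opposite one.

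SAP 4.2.5 also takes the EFS definition and censoring rules of an ivosidenib Phase III trial as reference. Those rules might settle precedence. They are cited rather than reproduced, so the point here is about the SAP's own text.

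Several limits stand:
- EFS is secondary and descriptive, with no hypothesis test, and it is not among the RP2D criteria in Protocol 4.1.1.
- Curves and landmark probabilities are planned for PFS and OS only, so for EFS it is the quartile shifts that matter. Quartiles at n=3 or 6 carry little information in any case.
- End-of-treatment marrow and tumor evaluation (Protocol 6.1.10.3 and Table 1) shrink the affected group. Patients who stop early with an adequate assessment after baseline, and whose baseline was also adequate, fall under Rule 4 only.
- The survival figures are not from this trial, which excludes ECOG above 2 and immediately life-threatening complications of leukemia.
- The missing-baseline case is remote, because a baseline assessment is scheduled for every patient.

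These limits bear on size. They do not remove the overlap.

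**Conclusion.** The concern holds. For a patient who dies, or stops before 24 weeks without CR, and has no adequate assessment, Table 4 gives two opposite outcomes on the same date and the SAP does not choose between them. Taken literally, Rule 9 censors deaths that the SAP's own EFS definition counts as events; PFS and best overall response do not have this gap.

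The effect is conditional. It is nil if Rule 4 is applied first. If Rule 9 is applied first, with the usual handling of ties, Day 1 EFS rises by 1/n per affected patient. One patient can then move a reported quartile at n=3 or n=6, and two can at n=12, for the CR counts shown. How many patients are affected in this trial cannot be known from the documents. This should be fixed before the analysis is programmed; it does not affect the primary safety objective.

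**What to change.** In SAP 4.2.5:
1. Limit Table 4 Rule 9 and Table 5 hierarchy 1 to patients who have neither died nor discontinued treatment. The death clause matches PFS Table 7 Rule 3; the discontinuation clause follows EFS Rule 4 and goes further than PFS does.
2. Add one sentence: event Rules 1–4 take precedence over Rule 9. This also covers a patient on treatment for at least 24 weeks with no adequate assessment, who otherwise meets both Rule 3 and Rule 9.
3. State that a missing baseline alone does not censor a patient with a documented CR followed by relapse or death.
4. Report the number of patients falling under Rule 9, by dose level.

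At the final analysis Rule 9 may then apply to almost nobody, which is acceptable: what is left is patients still active with no assessment. The cost is a few words in two tables, two sentences and a programming check. No new data are needed. EFS may look less favorable than it would with Rule 9 applied first.

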4.2.6. Overall Survival

Overall Survival (OS) is defined as the time (months) from the start of study treatment from Cycle 1 in continuous cycle (i.e. not from the date of single oral dose from the PK week for the dose escalation part) until the date of death due to any cause. OS is calculated as (date of death or last known alive – date of first administration of study treatment from Cycle 1 + 1)/30.4375.

In the rare case, if date of death is missing, date of death will be imputed using rules in [Section 5.1.2](#).

Patients who do not die during the study will be censored at last known alive date. OS will not be censored at the date of initiating subsequent anticancer medication if a patient receives subsequent anticancer medication after discontinuation of the study drugs. Reasons for censoring are included in [Table 6](#) following the hierarchy.

Table 6 OS Censoring Reasons and Hierarchy

Hierarchy	Condition	Censoring Reason
1	No event and Withdrawal of consent in any disposition page or survival follow-up page	Withdrawal of consent
2	No event and lost to follow-up in any disposition page or survival follow-up page	Lost to follow-up
3	No event and none of the conditions in the prior hierarchy are met	Alive

OS=overall survival.

